9.2 L-PF SCORING INSTRUCTIONS

9.2.1 Symptoms

9.2.1.1 Dyspnea (items 1-12)

For items 1, 2, 4-10, and 12:

- if “No” is ticked and “A” is ticked, the score is 5
- if “No” is ticked and “B” is ticked, the item is not scored and does not contribute to the denominator
- if “No” is ticked and neither “A” nor “B” is ticked, the item is counted as missing and handled per “Instructions for Missing Items”. Items for which this occurs DO contribute to the denominator

For items 3 and 11:

- scores equal whichever box is ticked (0-4)

$$\text{Dyspnea Symptom Score} = \frac{\text{sum of responses from items 1 - 12}}{\text{total score possible for items without "No"/"B" response}} \times 100$$

9.2.1.2 Cough (items 13-18)

$$\text{Cough Symptom Score} = \frac{\text{sum of responses from items 13 - 18}}{24} \times 100$$

9.2.1.3 Energy (items 19-23)

For items 19-22:

- scores equal whichever box is ticked (0-4)

For item 23:

- if “Yes” is ticked, score equals whichever box is ticked (0-4)
- if “No” is ticked, the item is not scored and does NOT contribute to denominator

$$\text{Energy Symptom Score} = \frac{\text{sum of responses from items 19 - 23}}{\text{total score possible (20 or 16 if response for 23 is "No")}} \times 100$$

9.2.1.4 Symptoms Total Score

$$\text{Symptoms Total Score} = \frac{(\text{Dyspnea Symptom} + \text{Cough Symptom} + \text{Energy Symptom})}{3}$$

9.2.2 Impacts

9.2.2.1 Dyspnea (items 1-6)

$$\text{Dyspnea Impact Score} = \frac{\text{sum of responses from items } 1 - 6}{24} \times 100$$

9.2.2.2 Cough (items 7-11)

$$\text{Cough Impact Score} = \frac{\text{sum of responses from items } 7 - 11}{20} \times 100$$

9.2.2.3 Energy (items 13-14)

$$\text{Energy Impact Score} = \frac{\text{sum of responses from items } 13 - 14}{8} \times 100$$

9.2.2.4 Global (items 12, 15-21)

$$\text{Global Impact Score} = \frac{\text{sum of responses from items } 12, 15 - 21}{32} \times 100$$

9.2.2.5 Impacts Total Score

$$\text{Impacts Total Score} = \frac{(\text{Dyspnea Impact} + \text{Cough Impact} + \text{Energy Impact} + \text{Global Impact})}{4}$$

9.3 PF-IQOLS SCORING INSTRUCTIONS

9.3.1 Summary score

The scoring of the PF-IQOLS follows Flanagan's practice in that a very straightforward 5-point Likert-type rating scale is used, and the scoring is analogous to that of the QOLS – i.e., the summary score is the average of the individual dimension ratings 1-16. The response option for all items ranges from 1 (no negative effect at all) to 5 (extremely negative effect). Therefore the score range for the summary score is 1.0-5.0. The individual item scores can be directly taken from the answered questions in the questionnaire. Please see more details in the questionnaire ([Figure 9.3.1: 1](#) and [Figure 9.3.1: 2](#))

Over the past four weeks, how much did your pulmonary fibrosis negatively affect your life in each of the following areas?

Consider the effects of the pulmonary fibrosis itself, the medications you take for pulmonary fibrosis (including supplemental oxygen if you use it), and anything you did to avoid, treat, or get medical care for symptoms of pulmonary fibrosis.

	No Negative Effect At All 1	Slightly Negative Effect 2	Moderately Negative Effect 3	Very Negative Effect 4	Extremely Negative Effect 5
1. Material comforts — things like a desirable home, good food, possessions, conveniences, an increasing income, and security for the future.	1	2	3	4	5
2. Health and personal safety — being physically fit and vigorous, free from anxiety and distress, and avoiding bodily harm.	1	2	3	4	5
3. Relationships with your parents, brothers, sisters, and other relatives — communicating, visiting, and doing things with, understanding, and helping and being helped by your relatives.	1	2	3	4	5
4. Having and raising children — being a parent and helping, teaching, and caring for your children.	1	2	3	4	5
5. Close relationship with a husband, wife, or partner	1	2	3	4	5
6. Close friends — sharing activities, interests, and views; being accepted, visiting, giving and receiving help, love, trust, support, guidance.	1	2	3	4	5
7. Helping and encouraging others — adults or children other than relatives or close friends. These can be your own efforts or efforts as a member of a church, club, or volunteer group.	1	2	3	4	5
8. Participation in activities relating to local and national government and public affairs.	1	2	3	4	5

IQOLS scale developed by [name]. Dimensions from Flanagan, JC. *American Psychologist*. 1978;33:138-147, with addition by Burckhardt, CS, et al. *Research in Nursing & Health* 1989; 12:347-35.

Figure 9.3.1: 1 Part I of the PF-IQOLS Questionnaire.

Over the past four weeks, how much did your pulmonary fibrosis negatively affect your life in each of the following areas?

	No Negative Effect At All 1	Slightly Negative Effect 2	Moderately Negative Effect 3	Very Negative Effect 4	Extremely Negative Effect 5
9. Learning , attending school, improving your understanding, or gaining additional knowledge.	1	2	3	4	5
10. Understanding yourself — knowing your assets and limitations, knowing what life is all about and making decisions on major life activities. For some people, this includes religious or spiritual experiences; for others, it is developing an attitude toward life or a philosophy.	1	2	3	4	5
11. Independence — doing for yourself: being able to take care of and make decisions about your daily needs, personal care, where you live, and your financial affairs.	1	2	3	4	5
12. Work in a job or at home that is interesting, rewarding, and worthwhile.	1	2	3	4	5
13. Expressing yourself in a creative manner in music, art, writing, photography, practical activities, or in leisure time activities	1	2	3	4	5
14. Socializing — meeting other people, doing things with them, and hosting or attending parties or other social gatherings.	1	2	3	4	5
15. Reading, listening to music, or observing sporting events or entertainment.	1	2	3	4	5
16. Participation in active recreation such as playing sports, traveling and sightseeing, playing games or cards, singing, dancing, playing an instrument, acting, and other such activities.	1	2	3	4	5

IQOLS scale developed by [name]. Dimensions from Flanagan, JC. *American Psychologist*. 1978;33:138-147, with addition by Burckhardt, CS, et al. *Research in Nursing & Health* 1989; 12:347-35.

Figure 9.3.1: 2 Part II of the PF-IQOLS Questionnaire

9.4 ADDITIONAL ANALYSES FOR REGIONAL SUBMISSIONS

For the Japanese submission, the analyses will be conducted according to “Format for Preparing the Common Technical Document for Submission of New Drug Applications to Reduce Total Review Time” ([17](#)).

For the analysis due to local regulatory submission ([21](#)), the following patient subsets are defined.

Table 9.4: 1 Patient subset definitions for local regulatory submission in Asia

Category	Patient Subset
Local	
Japanese patients Chinese patients
 
The patients in each local site and Asian race will be included (e.g. Japanese patients: Site in Japan and single race is Asian). If Asian race will be “Multiple” and multiple race responder will be “Asian & xxx”, the patient will be handled as “Asian”. (e.g. Japan: Site in Japan and multiple race is Asian & White.)

East Asia	
East Asian patients
 
The patients from East Asian countries or region (i.e. Japan, Korea and China) with Asian race. Asian race definition is same definition as for local category.

Some outputs from CTR Section 15 or section 16 will be selected for the patient subsets defined in Table 9.4: 1. Due to small sample size of some of the patient subsets, some tables might be skipped. The same analysis models as defined in [Section 7](#) will be used. A detailed plan will be described in the CSAP. In the event of non-convergence, the same methods as described in [Section 7.4.1](#) will be used to overcome the issue. But in case of very limited number of patients, the more simplified model or descriptive statistics may be used if convergence is not achieved via the described methods in [Section 7](#). These patient subset analyses will not be produced as part of the CTR appendix and will not be described in the text of the CTR.

Other subset analysis than described in Table 9.4: 1 may be conducted in response to regulatory requests and the detailed plan for that case will be described in the CSAP.

9.5 PROGRAMMING CODE FOR INFERENTIAL ANALYSIS

9.5.1 Primary endpoint model

The key code is given below. Time is defined as duration since first trial drug intake divided by 365.25. Visit is the visit number. For the co-primary population, please remove HRCT as variable from the model.

```

ODS OUTPUT estimates=estimateout;
PROC MIXED data=FVC cl method=reml order= formatted covtest;
  CLASS patient treatment hrct;
  MODEL endpoint= treatment treatment*time hrct fvcbaseline fvcbaseline*time /solution CL
    ddfm=KR;
  RANDOM intercept time/ type=un subject=patient;
  ESTIMATE 'Nintedanib' fvcbaseline*time meanbase treatment*time 0 1 / e CL;
  ESTIMATE 'Placebo' fvcbaseline*time meanbase treatment*time 1 0 / e CL;
  ESTIMATE 'Nintedanib 150mg bid – Placebo' treatment*time -1 1 / e CL;
RUN;
ODS OUTPUT CLOSE;

```

9.5.2 Primary endpoint subgroup analysis model:

Example subgroup used: Gender (Male / Female).

```

ODS OUTPUT estimates=estimatesout Contrasts=contrastsout ;
PROC MIXED data=FVC cl method=reml order= formatted covtest;
  CLASS patient treatment hrct subgroup;
  MODEL endpoint= treatment*subgroup treatment*subgroup*time
    hrct fvcbaseline fvcbaseline*time
    /solution CL ddfm=KR;
  RANDOM intercept time/ type=un subject=patient;
  ESTIMATE 'Nintedanib - Female' fvcbaseline*time meanbase treatment * subgroup *time 0 0 1 0
    / cl e;
  ESTIMATE 'Placebo - Female' fvcbaseline*time meanbase treatment * subgroup *time 1 0 0 0
    / cl e;
  ESTIMATE 'Nintedanib - Male' fvcbaseline*time meanbase treatment * subgroup *time 0 0 0 1 /
    cl e;
  ESTIMATE 'Placebo - Male' fvcbaseline*time meanbase treatment * subgroup *time 0 1 0 0
    / cl e;
  ESTIMATE 'Nintedanib – Placebo Female' subgroup * treatment *time
    -1 0 1 0 / e CL;
  ESTIMATE 'Nintedanib – Placebo Male' subgroup * treatment *time
    0 -1 0 1 / e CL;
  CONTRAST 'F-test of heterogeneity at 52 weeks'
    subgroup * treatment *time -1 1 1 -1 / e;
RUN;
ODS OUTPUT CLOSE ;

```

9.5.3 Implementation of multiple imputation:

The following steps provide a guidance of how missing FVC data at week 52 will be implemented in patients of pattern 3 and 4 using multiple imputation. Refer to [Table 7.4.2.1.2: 1](#) for the description of patterns and the different sensitivity analyses regarding handling of missing data.

1. Run the MMRM of the primary analysis (either including patients of pattern 2 only for sensitivity analyses 1 and 2 or on all patients for sensitivity analysis 3) to get the slope

estimates (SE) by treatment group. Let $\hat{\beta}_D$ and $\hat{\sigma}_D$ denote the slope (SE) estimates in Nintedanib 150 mg and $\hat{\beta}_P$ and $\hat{\sigma}_P$ the slope (SE) estimates in placebo.

2. Let β_D and β_P represent the true slopes in drug and placebo respectively with $f(\beta_D) \sim N(\hat{\beta}_D, \hat{\sigma}^2_D)$ and with $f(\beta_P) \sim N(\hat{\beta}_P, \hat{\sigma}^2_P)$, using the slope (SE) estimates obtained in step 1.
3. Imputation of missing week 52 data in patients of pattern 3:

Multiple impute missing values (1000 imputations per patient). To do so, draw random slopes from the distributions defined in step 2. Considering that the withdrawal of a patient leading to missing data can occur at any time during the study, the timepoint of the last available FVC value has to be taken into account to impute the missing FVC value at 52 weeks.

$$\text{FVC week 52 imputed}_{ij} = \text{last FVC value available}_i + \hat{\beta}_{ij}(\text{time between date of last FVC value available}_i \text{ and planned 52 week timepoint [days]})$$

where i denotes the indicator of the i^{th} patient, j the indicator of the j^{th} imputation and $\hat{\beta}_{ij}$ denotes a random slope sampled from the distribution mentioned in step 3a for the i^{th} patient in the j^{th} imputation. Depending on the sensitivity analysis, use either random slopes drawn from $f(\beta_D)$ for patients randomised to Nintedanib 150 mg in sensitivity analysis 1 or $f(\beta_P)$ for all patients in sensitivity analyses 2 and 3.

4. Imputation of missing week 52 data in patients of pattern 4:

Multiple impute missing values (1000 imputations per patient). To do so, draw random slopes from the truncated distribution $f(\beta_P)/2$ restricted to the interval $(-\infty, \hat{\beta}_P]$ defined in step 2.

See step 3 for further details on how to use these slopes to impute the missing values at week 52.

5. Run the MMRM of the primary analysis on each imputed dataset, using a "by _IMPUTATION_" statement.
6. Combine the estimates obtained in step 5 using PROC MIANALYZE.

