7.6 RANDOMIZATION

Within each randomization HRCT pattern stratum ("UIP-like fibrotic pattern only" or "Other fibrotic patterns"), patients will be randomized in blocks to double-blind treatment in a 1:1 ratio. Approximately equal numbers of patients will be randomized to each treatment group. The randomization system will include caps for the two HRCT pattern strata so that approximately two thirds of the patients are randomized to the "UIP-like fibrotic pattern only" stratum and one third is randomized to the "Other fibrotic patterns" stratum (i.e. approximately 400 and 200 patients to each stratum, respectively). As a consequence of these caps randomization might be put on hold in one stratum temporarily and may mean that screened patients cannot be randomized immediately.

The Sponsor will arrange for the randomization and the packaging and labelling of trial medication. The randomization list will be generated using a validated system, which involves a pseudo-random number generator so that the resulting treatment will be both reproducible and non-predictable. The block size will be documented in the CTR. Access to the codes will be controlled and documented.

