7.7 DETERMINATION OF SAMPLE SIZE

Lack of published data from randomized clinical trials in patients with PF-ILD leads to uncertainty both on the rate of forced vital capacity (FVC) decline and on its variability in the planned study population.

The main assumption of the study is that patients with PF-ILD, independent from their original ILD classification, at some point in time, exhibit a progressive fibrosing phenotype. In this group of patients with PF-ILD, the disease behaviour over time (e.g. lung function, mortality) appears to follow a course similar to IPF, a typical example of PF-ILD.

Based on the existing literature for IPF, the observed mean values for the annual rate of decline in FVC or the FVC change from baseline to 45–52 weeks in patients treated with placebo was approximately between 140 mL and 250 mL (see [Section 10.5](#)).

The currently available data in different ILDs show that the ILD injury pattern, in particular the presence of UIP, is associated with worse prognosis ([P11-07084](#), [R10-6539](#), [R16-0554](#), [R15-3264](#), [R16-1567](#), [R14-3529](#), [R16-0752](#), [R16-1568](#)). Based on this, the study will be enriched for patients with UIP pattern. UIP pattern will be defined based on HRCT using the same HRCT criteria as in the Phase III IPF trials for nintedanib ([P15-04977](#), [P15-05695](#)) and described in [Section 1.1](#). Since these criteria differ slightly from the current definition of radiologic UIP provided in the ATS/ERS guidelines (P11-07084), patients with screening HRCT meeting the protocol criteria for UIP will be referred to as “patients with HRCT with UIP-like fibrotic pattern only”. Patients with HRCT patterns not meeting the protocol criteria for UIP will be referred to as “patients with other HRCT fibrotic patterns”.

For scenario planning for the sample size calculation, a rate of decline of 150-200 mL/year has been assumed for PF-ILD patients with HRCT with UIP-like fibrotic pattern only. For the patients with other HRCT fibrotic patterns, the FVC rate of decline is assumed to be slightly lower than in PF-ILD patients with HRCT with UIP-like fibrotic pattern only: between 120 and 150 mL/year.

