In order to maintain an overall type 1 error rate of 5%, a Hochberg procedure will be used ([R97-1003](#)). This multiplicity adjustment strongly controls the overall Type I error rate in clinical trials with a targeted subpopulation ([R16-1041](#)). For the primary endpoint, statistical significance will be declared if the analyses in both co-primary populations are significant at the two-sided 5% level, **or** if the analyses in either co-primary population are statistically significant at the two-sided 2.5% level. Given the proposed design properties it is calculated that applying this procedure, the overall alpha spent will be 4.35% so the overall Type I error control is below 5%. This is based upon the summation of the probabilities of rejecting H_0 under various combinations of results for the co-primary populations within the Hochberg procedure (calculated using SAS® Version 9.4, see [Appendix 10.6](#) for details).

[Table 7.7: 1](#) below presents the power properties of this study for several scenarios for the treatment effect in the two co-primary populations.

Table 7.7: 1: Power properties for several scenarios for the treatment effect in the two co-primary populations

	Patients with HRCT with UIP- like fibrotic pattern only Co-primary	Patients with other HRCT fibrotic patterns	Overall patient population Co-primary	
Scenario 1				
Assumed treatment difference in absolute change in FVC in mL/year (SD)	100 (300)	75 (400)	92 (337)	
Individual test power	90.2%		90.3%	
Overall Power [*]				92.6%
Scenario 2				
Assumed treatment difference in absolute change in FVC in mL/year (SD)	75 (300)	60 (400)	70 (337)	
Individual test power	67.2%		68.2%	
Overall Power [*]				72.4%
Scenario 3				
Assumed treatment difference in absolute change in FVC in mL/year (SD)	75 (300)	75 (400)	75 (337)	
Individual test power	68.2%		73.4%	
Overall Power [*]				75.8%

FVC, forced vital capacity; SD, standard deviation.

Power calculations are based on Hochberg procedure at the overall type 1 error rate of 5% (two-sided), with 200 patients with HRCT with UIP-like fibrotic pattern only and 100 patients with other HRCT fibrotic patterns per treatment group.

*The overall power is the probability of concluding statistical significance for either of the co-primary populations.

Power calculated using SAS[®] Version 9.4 (see [Appendix 10.6](#) for details)

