7.4.1 Primary analysis

The primary analysis will be based on the TS (according to randomised treatment), using all available data from baseline (excluded) up to Week 52, including visits done after premature treatment discontinuation, EOT visits and follow-up visits done before Week 52 (i.e. including all measurements after first drug intake and before or on day 373). Patients will be analysed based on the fibrotic pattern data entered in the eCRF, which may not necessarily coincide with data used for randomisation. Details on sensitivity analyses can be found in [Section 7.4.2](#).

The primary analysis uses a restricted maximum likelihood (REML) based approach with a random slope and intercept model. The analysis will include the fixed, categorical effects of treatment, HRCT pattern, fixed continuous effects of time and baseline FVC (ml) as well as the treatment-by-time and baseline-by-time interactions. Random effects will be included for patient response for both time and intercept.

The statistical model can be written as follows:

$$y_{ijkm} = (\alpha + a_i + \vartheta_m + \beta_0 S_i + \tau_k) + (\gamma + g_i + \beta_s S_i + \varphi_k) t_{ij} + e_{ij}$$

$$(a_i, g_i) \sim N_2 (\mathbf{0}, \Sigma)$$

$$e_{ij} \stackrel{iid}{\sim} N (0, \sigma^2)$$

The components of the model are as follows:

y_{ijkm}	=	response variable for patient i with HRCT pattern m at visit j receiving treatment k
α	=	mean patient intercept
a_i	=	random intercept effect for patient i, $i=1,2,\dots$
ϑ_m	=	intercept coefficient of HRCT pattern (“other HRCT fibrotic patterns” as the class reference)
β_0	=	intercept coefficient of baseline FVC (ml)
S_i	=	baseline FVC (ml) measurement for patient i
τ_k	=	intercept coefficient of the effect of treatment k, $k=1,2$
γ	=	mean patient slope
g_i	=	random slope effect for patient i
β_s	=	slope coefficient of baseline FVC (ml)

φ_k = slope coefficient of the effect of treatment k
 t_{ij} = time of measurement j for patient i, $j = 1, 2, \dots, J$
 e_{ij} = the random error associated with the j^{th} visit of patient i. Measurement errors are independent and normally distributed with mean 0 and variance σ^2 , and uncorrelated with a_i and g_i .
 Σ = a 2x2 unstructured covariance matrix

For the co-primary evaluation of FVC (in ml over 52 weeks) in patients with “HRCT with UIP-like fibrotic pattern only”, the following model will be utilised:

$$\begin{aligned}

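### The overall-population primary model adjusts the FVC intercept but not the FVC slope for HRCT pattern, the only stratification factor, at a small cost in precision

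*SAP*

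**What the plan says.** Randomisation is stratified by HRCT pattern only (Protocol 7.6): within each stratum "patients will be randomized in blocks to double-blind treatment in a 1:1 ratio". Protocol 7.1, 7.3 and 7.3.1 name baseline FVC and HRCT pattern as covariates in the overall-population analysis, without saying whether they act on the intercept, the slope or both.

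The SAP settles this. In the 7.4.1 equation the HRCT term stands in the intercept bracket and is labelled "intercept coefficient of HRCT pattern". The slope bracket holds the mean slope, the patient's random slope, baseline FVC and treatment. The code in 9.5.1 agrees: its fixed effects are "treatment treatment*time hrct fvcbaseline fvcbaseline*time", with no hrct*time. The treatment comparison is read from the treatment-by-time coefficient.

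Protocol 7.7 plans on declines of 150-200 mL/year in UIP-like patients. For the other patterns it says that "the FVC rate of decline is assumed to be slightly lower than in PF-ILD patients with HRCT with UIP-like fibrotic pattern only", giving 120 to 150 mL/year. It assumes a relative reduction of about 50% in both groups.

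Pattern-specific slopes do appear elsewhere. The model is fitted separately in UIP-like patients (co-primary) and in other-pattern patients (complementary, no p-value). SAP 7.4.3 also fits one model with HRCT pattern as a subgroup.

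**The concern.** A covariate that enters only the intercept explains differences in FVC level. It does not explain differences in rate of change, which is what is tested. If UIP-like patients decline faster, that difference stays in the random-slope variance, and the SE of the overall-population treatment contrast is larger than it need be. The usual reason for putting a stratification factor in the analysis is to recover that precision, and here it is not recovered. The SAP lets baseline FVC act on the slope and gives no reason for treating the stratification factor differently.

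The planning is also out of step with the model. The overall SD of 337 mL/year equals the pooled within-stratum SD, which is the SD of a slope already adjusted for stratum. What is at stake is a little power in one of the two co-primary populations.

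**Working it through.** **Inputs** (Protocol 7.7 unless stated)
- Sample size: "with 200 patients with HRCT with UIP-like fibrotic pattern only and 100 patients with other HRCT fibrotic patterns per treatment group", so 300 per arm with UIP-like share f = 2/3.
- SD: 300 (UIP-like) and 400 (other) mL/year.
- Placebo declines: 150-200 and 120-150 mL/year, with about 50% reduction on nintedanib in both.
- Testing: Hochberg, both populations at 5% or "if the analyses in either co-primary population are statistically significant at the two-sided 2.5% level".
- Correlation of the two test statistics: sqrt(0.667), as in Appendix 10.6.

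**1. The plan's own figures.** Running the Appendix 10.6 formulas gives, for UIP-like / overall / either:
- scenario 1: 90.18 / 90.30 / 92.55%
- scenario 2: 67.16 / 68.20 / 72.41%
- scenario 3: 68.23 / 73.41 / 75.84%

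These match Table 7.7: 1. Two-sided alpha is 2 × 2.174% = 4.35%, as stated ("the overall alpha spent will be 4.35" per cent).

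**2. Which SD is 337?** sqrt((2 × 300² + 400²)/3) = sqrt(113,333) = 336.65. This contains no between-stratum slope variance.

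**3. Variance left in by omitting hrct*time.** For a placebo gap D, the between-stratum variance is f(1−f)D² = (2/9)D² on placebo and (2/9)(D/2)² on nintedanib. Averaged over arms:
- D = 30: (200 + 50)/2 = 125
- D = 50: (556 + 139)/2 = 347
- D = 80: (1,422 + 356)/2 = 889

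Divide by 113,333 for the relative variance. SE = SD × sqrt(2/300), which is 27.487 with the term. The overall effect is (2/3)(UIP-like decline/2) + (1/3)(other decline/2).

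| Placebo declines | Effect | Added variance | SD without term | SE without term | SE excess | Hochberg power, overall: with → without | Either population: with → without |
|---|---|---|---|---|---|---|---|
| 150 vs 120 | 70.0 | 0.11% | 336.84 | 27.503 | 0.06% | 68.28 → 68.24% | 72.46 → 72.43% |
| 200 vs 150 | 91.7 | 0.31% | 337.17 | 27.529 | 0.15% | 90.17 → 90.10% | 92.49 → 92.45% |
| 200 vs 120 | 86.7 | 0.78% | 337.97 | 27.595 | 0.39% | 87.16 → 86.93% | 91.17 → 91.08% |

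Before rounding, the overall-population losses are 0.04, 0.08 and 0.23 points. With equal declines of 150 the loss is zero.

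These losses are upper figures, because they treat the larger SE as real sampling variability. With randomisation blocked within strata, the estimate itself varies no more; only the reported SE grows. Keeping the true SE at 27.487 and multiplying the overall-population critical values by 336.84/336.65, 337.17/336.65 and 337.97/336.65 gives losses of about 0.03, 0.05 and 0.15 points.

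**4. Type I error.** Under no effect, with the full gap in both arms, the SD without the term is sqrt(113,333 + (2/9)D²) = 336.95, 337.47 and 338.76 for D = 30, 50 and 80. The size of a nominal 5% test is 2[1 − Φ(1.96 × SD/336.65)] = 4.98%, 4.94% and 4.86%.

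**5. Bias check.** A 3,000-run simulation used complete data at the seven planned post-baseline visits. The intercept and residual SDs of 100 mL are assumptions, not document figures. The mean treatment-slope estimate was the same with and without the term: 71.09 (150 vs 120), 92.02 (200 vs 150) and 86.07 (200 vs 120). The model SE was 29.02 with the term, and 29.03, 29.06 and 29.12 without it.

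**The case against.** The strongest reply is that this is close to a modelling preference. The protocol promises only that HRCT pattern will be a covariate, and the SAP delivers that. The estimate is unchanged with complete data, and the test errs on the conservative side. At the gaps implied by Table 7.7: 1 (50, 30 and 0 mL/year) the loss is under a tenth of a point. Any slope difference will be visible in the complementary-population and HRCT-as-subgroup outputs. All of that stands, and it limits the point to a refinement. It does not remove it, because those pattern-specific outputs are supportive and do not change the SE of the confirmatory overall-population test.

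A reader might infer three stronger things.

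- **The primary analysis is biased or its error rate inflated.** Steps 4 and 5 show neither.
- **The missing-at-random assumption is compromised because drop-out differs by pattern.** The protocol says that UIP carries a worse prognosis, but gives no drop-out by pattern. Bias in the treatment contrast would also need pattern-related drop-out that differs between arms. The documents do not allow this to be sized, and the plan keeps off-treatment data and adds imputation and tipping-point analyses.
- **The loss is larger**, with 0.2%, 0.5% and 1.2% added variance for gaps of 30, 50 and 80. That applies the full gap in both arms, against the protocol's own assumption of a 50% reduction.

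It is also fair to say that the change is more than one line of code, since the sensitivity analyses reuse this model.

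**Conclusion.** The point holds as a small, inexpensive improvement to the overall-population model. The stratification factor does not adjust the tested slope. Over the protocol's own range of declines, the SE is about 0.05% to 0.4% too large and overall-population power at most about 0.23 points too low. The loss grows roughly with the square of the gap; about 200 mL/year in both arms would be needed to lose more than two points at a single two-sided 5% test with an effect of 92 mL/year.

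This rests on a 2:1 stratum mix, the planned SDs, the 50% relative effect, the plan's correlation between the two tests, and complete data. A slope difference is the protocol's main expectation, not a certainty: the ranges meet at 150 mL/year, and scenario 3 corresponds to equal slopes. The model uses the eCRF pattern, so the added term would adjust for the recorded pattern, which can differ from the IRT stratum in mis-stratified patients.

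**What to change.** Before unblinding:

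- Add hrct*time to the overall-population MODEL statement in SAP 9.5.1, and a slope coefficient for HRCT pattern to the overall-population equation in 7.4.1.
- Form the two arm-specific slope ESTIMATEs at the observed stratum proportions. Leave the treatment*time contrast unchanged.
- Carry the same term into the analyses that reuse the primary model: on-treatment (7.4.2.1.1), multiple imputation (7.4.2.1.2 and 9.5.3) and tipping point (9.12.1). For 9.5.3, state whether imputed slopes are drawn by arm only or by arm and pattern.
- Leave the UIP-like and complementary-population models as they are.

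The cost is one fixed effect in about 600 patients, one equation term and small edits to dependent code. No protocol text is contradicted. The model would still estimate one common absolute treatment effect across patterns; the HRCT-as-subgroup analysis remains the place to examine differences in that.

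If unblinding has occurred, keep the specified model as primary and report the version with hrct*time as a labelled sensitivity analysis.
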